8.6.4 Demographic characteristics, screening and baseline

Descriptive statistics and listings for each variable per visit (Screening Visit or Baseline Visit) will be performed.

This analysis will be performed using Safety set on ADO approach.

Results are presented by means of individual tables and listings for each of the variables described in section 8.6.1.

The comorbidities will be tabulated and listed by type of comorbidity. The number of patients with at least one comorbidity globally and by type of comorbidity will be described. The following type of comorbidities will be considered: myocardial infarction, deep venous thrombosis, pulmonary embolism, transient ischemic attack, ischemic stroke, cerebral hemorrhage, lower GI bleeding, diabetes mellitus type I, diabetes mellitus type II, hypertension, heart failure, phlebitis, gastrointestinal ulcer, angina pectoris, esophageal varices, upper GI bleeding and others (the description of others will be only listed).

8.6.5 Safety variables and other efficacy variables

8.6.5.1 Variables related to the primary outcomes

The binary variables related to primary outcomes (rate of AEs (CTCAE) ≥ 3 excluding palmar-plantar erythrodysthesia, rate of AEs, rate if related AEs, rate of SAEs, and rate of AEs leading to treatment discontinuation) will be described by means of rate and 95% CI calculated using the Clopper-Pearson exact method.

These analyses will be performed Safety set on ADO approach.

8.6.5.2 Variables related to the secondary outcomes

The analyses performed for the variables related to the secondary endpoints are described in the following sections.

8.6.5.2.1 Binary variables

The binary variables related to the secondary outcomes (see section 8.4.2 for more details) will be described by means of rate and 95% CI calculated using the Clopper-Pearson exact method.

These binary variables are the following:

- ORR defined as the best response.
- Rate of patients who develop new extrahepatic spread.
- Progression rate in general and by Pattern of progression (see section 8.3.2 for more details).

These analyses will be performed using Safety set on ADO approach. For the ORR (as a best response) the missing data will be imputed as a failure.

The timing of response will be plotted using a Swimmer plot.

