| Study procedures and examinations | | | | | | | |
| Physical examination | x | x | x | * | x | x | |
| ECOG performance status | x | x | x | * | x | x | |
| 12-lead ECG ⁴ | x | | | | | x | |
| Vital signs ⁵ | x | x | x | * | x | x | |
| Assessment of AEs/SAEs | x | x | x | * | x | x | |
| Concomitant medications | x | x | x | * | x | x | |
| Diet and gut microbiota | x | | | | | | |
| | | | | | | | |
| Laboratory tests | | | | | | | |
| Serum chemistry ⁶ | x | x | x | * | x | x | |
| Hematology ⁷ | x | x | x | * | x | x | |
| Coagulation (PT, INR, PTT) | x | x | x | * | x | x | |
| HBsAg and HBsAb, HBcAb and HCV Ab; HBeAg and HBeAb, HBV DNA and HDV RNA and HDV Ab(HBV+ subjects only); HCV RNA (HCV+ subjects only) | x | | | | | x | |
| Thyroid function tests (TSH, free T3, free T4) | x | | | | | | |
| Urinalysis | x | x | x | * | | x | |
| Urine or serum pregnancy test (WOCBP) | x | | | | | | |
| | | | | | | | |
| Other procedures⁸ | | | | | | | |
| Other laboratory blood tests and assays ⁹ | | x | x Only in C1 | | x | | |
| Other liver tissue analysis ¹⁰ | x | | | * | x | | |
| Patient-reported Quality of Life (EQ-5D, EORTC-QLQ C30, EORTC-HCC18 and FACT-Hep) ¹¹ | | x | | | x | x | |
| Other stool tests and assays ¹² Day 1 | | x | | | | x | |

Sponsor's code: ACTION
EudraCT No: 2019-004991-20
Version: 4.0
Date: 15 July 2021
CONFIDENTIAL

Cycle 4 and in case of OR or PD

EOT: End of Treatment; **OR:** Objective Response; **PD:** Progressive Disease

¹ The time period between study entry and the commencement of protocol treatment is not to exceed 28 days.

² Follow-up visits could be on-site or phone visits after the last visit and will include survival data and liver cirrhosis complications evaluation every 3 months. If the patient does not start any other treatment after end of treatment, radiologic follow-up with the same scheduled will be preferred. Laboratory tests will be performed at the discretion of the treating investigator until death or the end of the study.

³ A biopsy will be performed at the time of progression whenever possible.

⁴ Note: The ECG should be performed within the 7 days prior the randomization. If the QTcF is > 500 ms in first ECG, a total of 3 ECGs should be performed. If the average of these 3 consecutive results for QTcF is ≤ 500 ms, the subject meets eligibility in this regard.

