8.5 STUDY ESTIMAND, HANDLING OF MISSING DATA AND CENSORING RULES

The handling of missing data will follow the principles specified in the ICH-E9 and the CPMP/EWP/1776/99 Rev1¹³. Guideline on Missing Data in confirmatory trials Guidelines. As per the ICH E9(R1) (Addendum on estimands and sensitivity analysis in clinical trials EMA/CHMP/ICH/436221/2017)¹⁴, the plan for the assessment of the Primary endpoint (PEP) (in this study includes the main secondary outcome) is described here after using the 4 attributes of the estimand:

1. Population: as described in protocol and section 8.1 of this SAP, all analyses will be carried out using Safety population.
2. Endpoints: (please see details on the endpoints definitions in section 8.3)
 - a. Non confirmatory primary endpoints (PEPs): the rate and type of:
 - Any AEs
 - Related-AEs
 - Rate of death
 - AEs leading to treatment discontinuation
 - Serious AEs (SAEs)
 - Rate of AEs (CTCAE)≥3 excluding palmar-plantar erythrodysthesia
 - b. Secondary endpoints (SEP):
 - ORR (main secondary outcome)
 - Overall survival (OS)
 - Time to progression (TTP)

- Pattern of progression
- Post-progression survival (PPS)
- Rate of patients who develop new extra-hepatic spread

3. **Intercurrent events (ICEs)**: the relevant intercurrent events expected to occur in this study includes the following situations and the method for handling will be the same for all of them due to the safety characteristics of the primary objective. The “Treatment Policy” strategy will be used, i.e., all observed data will be used regardless of the intercurrent event.

- a. No treatment initiation: exclusion from the analysis.
- b. Main estimand: any other situation regardless of the ICE (use of rescue medication, prohibited concomitant medication, treatment discontinuation, or any reason leading to study discontinuation): “Treatment Policy” strategy (i.e. all observed data will be considered regardless of any previous ICE).
- c. Supplementary estimand: for some relevant efficacy secondary endpoints, data after ICEs will be censored (see table below) and will be based on the while on treatment strategy.

4. **Population-level summary**:

- a. Estimation of rates and 95%CI for the PEPs by means of Clopper-Pearson exact method will be used as the population-level summary (see sections 8.6.5.1 and 8.6.5.2.1).
- b. Time to event variables will be described using the Kaplan-Meier method (see section 8.6.5.2.2).

	Primary Estimand	Supplementary Estimand

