Primary endpoints		
Any AEs Related-AEs Rate of death AEs leading to treatment discontinuation Serious AEs (SAEs) Rate of AEs (CTCAE)≥3 excluding palmar-plantar erythrodysthesia	Treatment policy	None
Secondary endpoints		
ORR (main secondary outcome)	Treatment policy	While on treatment*
Overall survival (OS)		
Time to progression (TTP)		
Pattern of progression	Treatment policy	None
Rate of patients who develop new extra-hepatic spread		
Post-progression survival (PPS)		

*(censored after treatment ICEs)

The ORR rate will be handled using the Treatment Policy strategy. In the unexpected case of missing due to no radiologic assessment was conducted, the composite strategy will be applied by imputing to ORR to failure.

No formal imputations will be performed for any other variable. For the categorical variables the analyses will be based on the Available Data Only (ADO) approach. With regards to the continuous variables, mixed models^{15,16,17} are robust to the presence of missing at random (MAR) and conducts the analysis with all participants despite the presence of missingness. Of note, this method calculates the estimations based on the variance-covariance structure but without any formal imputations.

No formal imputation will be used for dates due to all post-inclusion dates are complete date.

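### The rate of new extrahepatic spread is a crude available-data proportion with no time-to-event analysis, while imaging after treatment is optional, so it is likely understated by an unknown amount

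*SAP*

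**What the plan says.** SAP 8.6.5.2.1 lists "Rate of patients who develop new extrahepatic spread" and "Progression rate in general and by Pattern of progression" among the binary secondary variables. These "will be described by means of rate and 95% CI calculated using the Clopper-Pearson exact method". On missing data the section adds: "These analyses will be performed using Safety set on ADO approach". SAP 8.5 says the same in general: "For the categorical variables the analyses will be based on the Available Data Only (ADO) approach". Only ORR has a rule for absent imaging (counted as failure).

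The estimand table in SAP 8.5 gives pattern of progression and new extrahepatic spread a treatment-policy strategy with no supplementary estimand. Under that strategy, "all observed data will be used regardless of the intercurrent event".

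Footnote 2 of Protocol Table 5, repeated under SAP 7.7, governs scans after treatment: "If the patient does not start any other treatment after end of treatment, radiologic follow-up with the same scheduled will be preferred". In the schedule as available, the disease-assessment row has no mark under end of treatment or follow-up. Protocol 4.1.5 makes survival follow-up compulsory after the drug is stopped.

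SAP 8.6.5.2.2 applies Kaplan-Meier to overall survival, time to first progression and post-progression survival. New extrahepatic spread is not on that list.

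**The concern.** New extrahepatic spread occurs over time and is seen only on a scan. A crude proportion estimates its probability correctly only if each patient is imaged until spread, death or a common cut-off. The treatment-policy label presumes scans after treatment stops, but the schedule does not secure them. Treatment may end for toxicity or by patient choice (Protocol 1.2.4.1), and part of the population is enrolled because it did not tolerate sorafenib, so stopping before spread is foreseeable. Such a patient, once scanned after baseline, stays in the denominator as a non-event however short the imaging was.

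The reported rate then depends on how long patients are imaged as well as on the disease, and the binomial interval does not reflect this. Protocol 9.1 plans indirect comparisons with external data through the study's 95% intervals, and SAP 8.7 repeats the secondary endpoints by first-line treatment. Unequal scan follow-up could distort both.

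**Working it through.** The documents give no expected value or precision target for either rate, so there is no planned figure to reproduce. What follows is an illustration with constant hazards.

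**Inputs for spread**
- Death hazard d = ln 2 / 10.2 = 0.068 per month (median overall survival with cabozantinib, Protocol 1.2.3).
- Horizon T = 15 months: enrolment ends July 2022 and all patients complete in October 2023 (Protocol synopsis, timelines).
- Spread hazard h = 0.04 per month: assumed.
- Hazard of imaging ending, c = 0 to 0.10 per month: assumed.

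**Formulas**
- Cumulative incidence = h/(h+d) × [1 − exp(−(h+d)T)]
- Crude rate, full denominator = h/(h+d+c) × [1 − exp(−(h+d+c)T)]
- Share whose scans stop first = c/(h+d+c) × [1 − exp(−(h+d+c)T)]

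**Spread.** Cumulative incidence = 0.04/0.108 × (1 − 0.198) = 29.7%.

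| c per month | Scans stop first | Crude rate | Gap (points) |
|---|---|---|---|
| 0 | 0% | 29.7% | 0 |
| 0.02 | 13% | 26.7% | 3 |
| 0.05 | 29% | 23.0% | 7 |
| 0.10 | 46% | 18.4% | 11 |

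With h = 0.02 the cumulative incidence is 16.7% and the crude rates are 14.9%, 12.7% and 10.0%, a gap of about 2 to 7 points.

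For scale, 10 events in 40 patients have a Clopper-Pearson interval of 12.7% to 41.2%, a half-width of about 14 points. A 3-point bias is minor against that; 11 points is not.

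**Progression.** The proxy is the 5.2-month median PFS (Protocol 1.2.3): ln 2 / 5.2 = 0.133 per month. That median already counts deaths. Treated as pure progression with no prior death, the true 15-month value is 86.5%, and the crude rate is 82.2% to 65.2% when scans stop first in 6% to 29% of patients (c = 0.01 to 0.06), a gap of 4 to 21 points. If 0.02 of the 0.133 is assigned to death before progression, progression has 0.113. The true value is then 0.113/0.133 × (1 − exp(−0.133 × 15)) = 73.5%. The crude rate is 69.9% to 55.4% for the same c, a gap of 4 to 18 points.

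**Denominator.** The available-data rule does not say whether a patient with no post-baseline scan is dropped. Suppose 28 of 40 are known to progress.
- 4 events missed, full denominator: 24/40 = 60.0% against a true 70.0%.
- 4 never-scanned patients dropped, none missed: 28/36 = 77.8%, where the truth lies between 28/40 = 70.0% and 32/40 = 80.0%.

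Dropping never-scanned patients can therefore move the rate up.

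**Why Kaplan-Meier with death censored is no remedy.** With h = 0.04, 1 − exp(−0.04 × 15) = 45.1%, against a true 29.7%.

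**The case against.** A reader might infer that scans stop at the end of treatment for many patients and that both rates are therefore biased low. The documents do not support that reading.

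- Nothing states how many patients lose imaging. Same-schedule scans are preferred while no new therapy has started. Protocol 6.1.6 asks sites to make all efforts to continue evaluations after withdrawal from treatment, and Appendix 3 asks the same for documenting progression after symptomatic deterioration. Treatment runs to symptomatic progression and may continue past radiologic progression (Protocol 6.1.7.1), so many first progressions will be captured on treatment.
- The direction is not certain, because the plan leaves the status of never-scanned patients open.
- Overall progression already has a Kaplan-Meier analysis with censoring at the last adequate assessment (SAP 8.5.1 and 8.6.5.2.2). SAP 8.3.2 names time to progression and pattern as secondary outcomes, not a progression rate.
- Counting a death as a non-event is not itself a fault: a cumulative incidence with death competing does so too, and the two agree when scanning is complete.
- The pattern rates do not enter the post-progression survival analysis, which is split by each patient's own pattern.
- SAP 8.6 declares the analyses non-inferential, and no decision rests on these rates.

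All of this stands and limits the point. It does not remove it for spread: that endpoint can appear after first progression, has no time-to-event counterpart, and relies on scans that are optional and not foreseen once another therapy starts.

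**Conclusion.** The point holds for new extrahepatic spread, where the crude rate is likely understated. It applies less strongly to the overall progression rate and to progression by pattern. The size is unknown: zero with complete imaging, and about 3 to 11 points if scans stop first in 13% to 46% of patients. Those figures rest on constant hazards, an assumed spread hazard, an assumed rate of imaging loss, and a death hazard borrowed from the phase 3 trial. Downward is the expected direction when patients with truncated imaging stay in the denominator. It is not guaranteed, because the available-data denominator is undefined, and that is a gap to close in its own right. The change is worth making because it is cheap and the endpoint is a named one.

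**What to change.** In SAP 8.6.5.2.1:

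1. **Spread.** Add, as the main estimate, an Aalen-Johansen cumulative incidence at 6 and 12 months with 95% CI.
2. **Death.** Count death as a competing event when it occurs while the patient is still under scheduled imaging, for example before two consecutive assessments are missed, in line with SAP 8.5.1. Otherwise censor at the last adequate scan. Do not reuse the TTP rule that censors death: it would remove the deaths that are meant to compete.
3. **Denominator.** State that patients with no post-baseline scan stay in the Safety set, censored at inclusion unless they die within that window.
4. **Progression.** Report the cumulative incidence of first progression overall in the same way. Describe patterns among first progressions by counts, allowing more than one per patient. Several patterns can appear on one scan, so they should not be modelled as competing event types.
5. **Description.** Keep the crude counts and report scan follow-up time. ORR stays binary.

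The cost is SAP wording and slightly more programming in standard software; no new data are needed. The method assumes that loss of scans is non-informative, which is doubtful when imaging ends through clinical decline and should be stated as a limitation.

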8.6.5.2.2 Time to event endpoint

The Kaplan-Meier method will be used to describe the survival functions the median and their 95% CI for time to event variables. These analyses will follow censoring rules as described in section 8.5.1.

These variables are the follow:

- Overall survival
- Time to the first progression
- Post-progression survival (in general and split by pattern progression)

These analyses will be performed using Safety set on ADO approach.

8.6.5.3 Other variables

A descriptive analysis will be performed for all variables of section 8.4.2 with the appropriate descriptive statistics (see section 8.6.1).

The continuous variables (laboratory parameters, vital signs and other continuous variables included in section 8.4.2) recruited by time (absolute values and absolute differences when applicable) will be analyzed by means of MMRM model specified in section 8.6.2. The same model with previous rank transformation will be applied to ordinal variables.

These analyses will be performed using Safety set on ADO approach.

The following sections describe the specific statistical analysis.

8.6.5.3.1 Tumor size

The tumor size of target lesions (absolute values, absolute difference and relative differences) will be described by time-point.

Also the absolute values and absolute differences will be analysed by means of MMRM model specified in section 8.6.2.

The relative change in tumor size will be plotted by means of Spider plot and the best change in the tumor size using a waterfall plot.

8.6.5.3.2 Duration of response

Additionally, the duration of response will be described with the appropriate descriptive statistics (see section 8.6.1).

The timing of response will be plotted using a Swimmer plot.

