8.3.2 Secondary outcomes

ORR will be the first relevant ranked secondary outcome:

- Defined as a partial or complete response at any time, i.e. the best response from inclusion along all follow-up.

The rest of secondary end points are:

1. Time to progression (TTP): time to the first progression, defined as the time from the inclusion date to progression (i.e. date of progression event or censoring – date of inclusion + 1).
2. Pattern of progression:
 - Intrahepatic growth (IHG): increased size of intrahepatic target lesions or progression of intrahepatic "non-target" lesions at baseline.
 - New intrahepatic lesion (NIH): emergence of new intrahepatic lesions
 - Extrahepatic growth (EHG): increased size of extrahepatic target lesions, progression of extrahepatic "non-target" lesions at baseline or progression of the existing vascular invasion.
3. Rate of patients who develop new extra-hepatic spread

4. Overall survival (OS): defined as the time from the inclusion date to death from any cause (i.e. date of death event or censoring – date of inclusion + 1).
5. Post-progression survival (PPS), for those patients who progressed, the time from the progression date to death from any cause (i.e. date of death event or censoring – date of 1st progression + 1).

Please see description of the censoring rules for time to event variables in section 8.5.1.

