8.6.1 General Descriptive Analysis

The results will be presented of standard methods¹⁸:

- Continuous variables: Mean, 95%CI of Mean (95% mean confidence interval), SD (standard deviation), minimum, P25 (percentile 25), Median, P75 (percentile 75), maximum and N.
- Categorical variables: total frequency and percentages and for each category.
- Ordinal variables with few categories (less than 10) will be described using two tables: one including continuous variables descriptive parameters (as long as the interpretation is reasonable) and the other including categorical variables descriptive parameters. For ordinal variables with >10 categories, the same approximation used for continuous variables will be applied.

Where applicable, these summaries will be provided by time-point (scheduled time-point) including the absolute differences from baseline. The data of unscheduled time-points will be only listed. Additionally, only for the size of tumor the relative difference from baseline will be also described.

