8.6.2 Specific Descriptive Analysis

For the binary variables related to the primary and secondary outcomes, the estimation of rates and 95% CI will be performed by means of Clopper-Pearson exact method.

The Kaplan-Meier method will be used to describe the time to event endpoints, the median and their 95% CI. Analysis will follow censoring rules as described in section 8.5.1.

The continuous efficacy variable recruited by time-point will be analysed as a descriptively by means of the MMRM approach, fitting time-point as a fixed effect, and the subject and error terms as random. The dependent variable will be the absolute values (or absolute change from baseline when applicable). The within-patient variance-covariance matrix will be assumed to be unstructured. If this analysis fails to converge, the following structures will be tested in the following order until convergence: AR(1) (Auto-Regressive first order), Toeplitz and CS (Compound Symmetry). Time-point effects have been estimated by means of Least Square Means (LSM) and their standard error (SE) and 95% CI. Time-course evolutions have been estimated by LSM and their SE and 95%CI. The same analysis with a previous rank transformation applies to ordinal variables.

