9 TABLES

For the table of safety variable and other efficacy variables (where applicable according to section 8.7) the results will be present for all subjects and by subgroup classification (within the same table).

9.1 Demographic characteristics, screening and baseline.

- Table 1. Study population.
- Table 2. Informed consent.
- Table 3. Demographic data and vital signs.
- Table 4. Clinical characteristics at HCC diagnosis.
- Table 5. Clinical characteristics at study entry.
- Table 6. Comorbidities. Number (%) of subjects reporting one or more Comorbidity (globally and by type of comorbidity).
- Table 7. First line treatment.
- Table 8. Selection criteria.

9.2 Safety variables and other efficacy variables.

- Table 9. **Primary outcomes.** Rate of AEs, SAEs, related-AEs, AEs leading to discontinuation, deaths and AEs (CTCAE) ≥ 3 excluding palmar-plantar erythrodysthesia.
- Table 10. **Secondary outcomes.** ORR and time to ORR.
- Table 11. **Secondary outcomes.** Overall survival.
- Table 12. **Secondary outcomes.** Time to progression (TTP)
- Table 13. **Secondary outcomes.** Pattern of progression.
- Table 14. **Secondary outcomes.** Post-progression survival.
- Table 15. **Secondary outcomes.** Rate of patient who develop new extrahepatic spread.
- Table 16. **Duration of response.**
- Table 17. BCLC staging system and CHILD-PUGH scale.
- Table 18. Tumor disease assessment (including tumor size).
- Table 19. Central test and stool test. Samples Yes/No.
- Table 20. Tumor biopsy.
- Table 21. Physical examination.
- Table 22. General examinations: vital signs, ECOG and oxygen saturation.
- Table 23. Laboratory test. Urinalysis.
- Table 24. Laboratory test. Hematology.
- Table 25. Laboratory test. Biochemistry and electrolyte.
- Table 26. Laboratory test. Thyroid functions.
- Table 27. Laboratory test. Specific laboratory test.
- Table 28. EQ-5D. Individual items.
- Table 29. EQ-5D. Three level items.
- Table 30. EQ-5D. Two level items.
- Table 31. EQ-5D. EQ VAS.
- Table 32. FACT-Hep. Directly items.
- Table 33. FACT-Hep. Subscales.
- Table 34. FACT-Hep. Total scores.
- Table 35. EORTC-QLQ-C30. Directly items.

Table 36. EORTC-QLQ-C30. Subscales.

Table 37. EORTC QLQ-HCC18. Directly items.

Table 38. EORTC QLQ-HCC18. Subscales.

Table 39. Exitus.

Table 40. Survival status variables.

Table 41. Cabozantinib treatment information.

Table 42. Visit control. Last visit by patient.

Table 43. Screen failure information.

Table 44. End of treatment.

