11 FIGURES

Figure 1. Overall survival. Survival plot.

Figure 2. Time to progression. Survival plot.

Figure 3. Post-progression survival. Survival plot.

Figure 4. Post-progression survival by pattern of progression. Survival plot.

Figure 5. Relative change in tumor size. Spider plot.

Figure 6. Best change in tumor size. Waterfall plot.

Figure 7. Time to response. Swimmer plot.

Figure 8. Duration of response. Survival plot.

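### Duration of response is given uncensored summary statistics while Figure 8 plans a survival plot of it, and the SAP has no event or censoring rule for it

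*SAP*

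**What the plan says.** SAP 8.6.5.3.2 states that "the duration of response will be described with the appropriate descriptive statistics (see section 8.6.1", and adds a swimmer plot for the timing of response. For a continuous variable, SAP 8.6.1 specifies: "Continuous variables: Mean, 95%CI of Mean (95% mean confidence interval), SD (standard deviation), minimum, P25 (percentile 25), Median, P75 (percentile 75), maximum and N". It makes no allowance for incomplete follow-up.

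Kaplan-Meier is in a different section, 8.6.2: "The Kaplan-Meier method will be used to describe the time to event endpoints, the median and their 95% CI". Section 8.6.5.2.2 lists the variables it applies to: overall survival, time to first progression, and "Post-progression survival (in general and split by pattern progression". Duration of response is not listed. Section 8.3.2 refers the reader to 8.5.1 for censoring: "Please see description of the censoring rules for time to event variables in section 8.5.1". Section 8.5.1 has rules for TTP, OS and PPS only.

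SAP section 9 names Table 16 simply "Duration of response", with no statistic. SAP section 11 has "Figure 8. Duration of response. Survival plot".

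Protocol Appendix 3 (Response duration) runs the interval from first CR or PR to first objectively documented recurrence or progression. It does not say what happens to a response that is ongoing at cutoff, or that ends in death or loss to follow-up.

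**The concern.** Duration of response is a time-to-event variable. A responder who has not progressed at the last scan contributes only a lower bound. The statistics in 8.6.1 need one complete value per patient, so someone must decide at analysis what to enter for an unfinished response, and the SAP does not say. Figure 8 needs the same decision in the form of event and censoring rules, and those are absent too.

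Two things are at stake. The table may understate how long responses last, and Table 16 and Figure 8 may give different answers for the same variable. Duration of response also qualifies ORR, which SAP 8.3.2 ranks first among the secondary outcomes.

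**Working it through.** **No plan figure to reproduce.** The documents give no assumed duration, number of events or precision for this variable. The calculation below is illustrative.

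**Direction.** Let T be the true duration and C the available follow-up after response, independent of T.
- Ongoing responses counted as ended: the analysed value is min(T, C), which never exceeds T, so the mean is too low.
- Ongoing responses left out: the chance of being kept, P(C ≥ T), falls as T rises, so long responses are lost preferentially and the mean is again too low.

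**Follow-up available.** The protocol synopsis gives enrolment from March 2020 to July 2022 and all patients completed in October 2023. Potential follow-up is therefore 43 months for the first patient and 15 for the last. Assuming response at about 3 months, C runs from 12 to 40 months, taken as uniform.

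**Size, administrative censoring only.** Assume exponential duration with median m, so the mean is μ = m / ln 2. Then

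P(T > C) = (μ/28) × (e^(−12/μ) − e^(−40/μ)), and E[min(T, C)] = μ × (1 − P(T > C)).

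For m = 6: μ = 8.66, and P(T > C) = (8.66/28) × (0.250 − 0.010) = 0.074. The raw mean is 8.66 × 0.926 = 8.0. Under this model the proportional fall in the mean equals the share censored. Simulation gives the same values and adds the medians (months):

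| True median | True mean | Censored | Mean, ongoing counted as ended | Mean, completed only | Median, counted as ended | Median, completed only |
|---|---|---|---|---|---|---|
| 4 | 5.8 | 2.5% | 5.6 | 5.3 | 4.0 | 3.9 |
| 6 | 8.7 | 7.4% | 8.0 | 7.1 | 6.0 | 5.4 |
| 9 | 13.0 | 16.3% | 10.9 | 8.8 | 9.0 | 7.0 |
| 12 | 17.3 | 24.8% | 13.0 | 10.0 | 12.0 | 8.2 |
| 18 | 26.0 | 38.5% | 16.0 | 11.2 | 15.1 | 9.5 |

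The median with ongoing responses counted as ended is correct up to 12 months, because every responder then has at least that much follow-up. Dropping ongoing responses does more harm: at m = 6 the mean falls by (8.7 − 7.1)/8.7 = 18%.

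**Size, with early loss of imaging.** Footnote 2 to Protocol Table 5 makes radiological follow-up after end of treatment only preferred, and only if no other treatment starts. Adding an assumed exponential loss with mean 12 months:

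| True median | True mean | Censored | Mean, counted as ended | Median, counted as ended |
|---|---|---|---|---|
| 4 | 5.8 | 32.9% | 3.9 | 2.7 |
| 6 | 8.7 | 42.9% | 4.9 | 3.5 |
| 12 | 17.3 | 61.1% | 6.8 | 4.9 |
| 18 | 26.0 | 70.5% | 7.7 | 5.7 |

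**How many responders.** The sample size is 40, and Protocol 1.2.3 reports an ORR of 4% with cabozantinib in the phase 3 trial.
- At 4%: 40 × 0.04 = 1.6 expected. P(at least 2) = 0.48, so the chance of none or one is 0.52. P(at least 5) = 0.02.
- At an assumed 10%: 4 expected, P(at least 5) = 0.37.
- At an assumed 20%: 8 expected, P(at least 5) = 0.92.

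**The case against.** The strongest defence is that the material for a correct reading is already planned: a survival plot (Figure 8), a swimmer plot (Figure 7) and a patient listing (Listing 11). With one or two responders, a reader will see each duration directly. Section 8.6.2 also applies Kaplan-Meier to time-to-event endpoints in general, and 8.6.5.3.2 asks for statistics that are appropriate. Duration of response is neither a primary nor a secondary outcome; it sits under other variables in 8.6.5.3, and no decision depends on it. This limits the weight but does not remove the conflict. Section 8.6.5.3.2 points to 8.6.1, not to 8.6.2, and Figure 8 cannot be drawn reproducibly without event and censoring rules.

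Two stronger readings should be resisted.
- A reader might infer that the SAP counts ongoing responses as ended. No section says so. They could equally be excluded or flagged; the handling is unspecified.
- A reader might infer that the raw median must be well short. Assuming follow-up after response spread evenly from zero to 12, 18 or 24 months, a true median of 6 months would appear as 3.3, 3.9 or 4.3. The protocol's timeline does not support a start at zero: the last patient has about 15 months, so a response within 6 months of entry still leaves about 9. Under administrative censoring alone, counting ongoing responses as ended leaves a 6-month median unbiased.

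It is also fair to say that Table 16 and Figure 8 differ only if some response is censored. If every responder has documented progression, their medians agree.

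**Conclusion.** The point holds as an inconsistency with an unspecified rule, and it is minor. The SAP text assigns duration of response a method that cannot represent censoring, while its own figure treats the variable as time-to-event. Any bias in the mean is downward, given follow-up independent of duration. Its size cannot be fixed from the documents: it ranges from a few per cent (short durations, administrative censoring, ongoing responses counted as ended) to more than half (long durations with early loss of imaging). These sizes rest on assumed exponential durations and assumed follow-up and loss patterns. At a 4% ORR the more immediate problem is that mean and SD say little about one or two patients. The point would matter more if the response rate were clearly higher.

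**What to change.** - **SAP 8.6.5.3.2 and Table 16:** replace the reference to 8.6.1 with Kaplan-Meier (median and 95% CI), from first CR or PR to documented progression. With fewer than 5 responders, give individual durations with ongoing status instead.
- **SAP 8.6.5.2.2:** add duration of response to the list of variables.
- **SAP 8.5.1:** add duration of response under the TTP rules, with time counted from first response rather than inclusion. These rules already cover no progression at cutoff (ongoing response), death without progression (censored at the last adequate assessment), loss to follow-up and missed assessments.
- **Reporting:** state the number of responses ongoing at cutoff next to the estimate.

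The cost is SAP wording only. No new data are needed, and Figure 8 requires the same rules in any case.
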